## **DESCRIPTION**

A pilot randomised controlled trial looking at the setting up of a one stop vein clinic for the treatment of varicose veins and assessing the quality-adjusted life years at 3 months of patients

This will be a pilot study which is designed to provide us with enough information for a potentially larger multicentre randomised controlled study.

## **OBJECTIVES**

- Primary Objective
  - Measure the quality-adjusted life years (QALY) gained at 3

months (using EuroQoL's EQ-5D) & AVVQ by patients randomised to treatment in the One Stop Vein Clinic with patients randomised to treatment in the normal care pathway

- Secondary Objective
  - Patient satisfaction with the service provided using the Picker patient experience questionnaire both post-operatively and at the 3 months follow-up (One Stop Vein Clinic versus Normal Care Pathway)
  - Measure and compare the quality of life scores using CIVIQ at 0 and 3 months in patients randomised to treatment in the One Stop Vein Clinic with patients randomised to the Normal Care Pathway
  - Record the time from referral to treatment (RTT)
  - Assess the cost-effectiveness of the One Stop Vein clinic compared to the normal care pathway
  - Record the time to return to normal activities and to work
  - Assess the estimated societal costs

## **BACKGROUND**

Varicose veins are very common conditions, affecting approximately 25% of the population.

Over 35,000 varicose vein procedures are currently carried out in the UK. However, with the new 2013 NICE guidelines, the Department of Health has estimated that this is set to increase to 50,000 per year. Waiting for varicose vein interventions has been shown to be detrimental to the severity of the condition and the quality of life of patients. Progression of varicose veins can also lead to complications such as leg ulcerations and can be costly to the health service. Over the past decade, new endovenous techniques have been introduced and these are felt to be cost-effective, especially, when performed in an outpatient or 'office-based' setting. At present, patients referred to the Vascular unit for consideration of management of their varicose veins have to attend the outpatient clinic at least twice prior to be listed for their procedure.

At present, patients referred to the Vascular Outpatient Clinics for consideration for varicose vein management have an initial appointment where the severity of the venous insufficiency is assessed clinically and, subsequently, have a venous Duplex scan to evaluate the extent and cause of any venous incompetence. If any treatable lesion is found, they are then added to the waiting list to come for the eventual varicose vein procedure. This means, they have to attend at least two outpatient appointments and attend another appointment for their venous scans, before actually attending for their varicose vein procedure. Waiting for varicose vein interventions has been shown to lead to worsening of their conditions both clinically and radiologically. In addition, the quality of life of patients waiting for elective surgery is adversely affected.

In order to evaluate patients' ideas and expectations with respect to the provision of varicose vein service in our unit, we conducted a survey of patients attending the Vascular Outpatient Clinic between March and June 2014. One hundred and six patients completed the anonymous questionnaire. Most were females (62.4%) with a mean age of  $51 \pm 15$  years. More than 90% of patients stated that the waiting time between a Vascular appointment and a venous scan should be no more than 1 month and 85% of patients believed varicose vein procedures should be received within 1 month of their Vascular clinic appointment. Ninety percent of patients were agreeable to attend a 'one-stop' vein clinic offering same day diagnosis and treatment. Patients were generally accepting of the fact that most procedures would be carried out under local anaesthetic (89%).

Hence, it appears that patients in our unit have a preference for a one stop clinic. This concept is not new and has been piloted in other specialities with good success - a one-stop carpal tunnel clinic as well as a one stop cataract clinic was shown to be feasible with good

patient satisfaction. Both laparoscopic and open inguinal hernia repairs, where patients received a general anaesthetic, have been carried out successfully using a one stop model offering same day diagnosis and treatment. There is currently already a 'see and treat' service for skin lumps operating at many NHS Trusts and there is already a one stop carpal tunnel service being provided at the Imperial College NHS Trust. It would appear that these one stop clinics have the advantage of reducing the number of unnecessary hospital visits as well as possibly leading to cost savings to the health service.

As a result, we intend to evaluate the one stop model within our own varicose vein service. We will assess the feasibility of having a one-stop vein clinic, where patients will be assessed, have their venous Duplex scans and, depending on the lesions shown, have their venous treatment on the same day.

The hypothetical benefits of such a stratagem are an improvement in patient satisfaction, a reduction in the number of appointments, the abolition of any waiting times as well as cost savings to the health savings.

## **METHODS**

GP referrals will be screened and patients meeting the inclusion criteria will be invited to take part in the trial.

They will be sent an information pack containing:

- Information leaflet about the trial
- Information about varicose veins, their treatments and a telephone number as a helpline
- The Aberdeen Varicose Vein Questionnaire (AVVQ), the Chronic Venous Disease Quality of Life Questionnaire (CIVIQ) and EuroQoL's quality of life questionnaire (EQ-5D)
- Consent form to participate in the study

Patients agreeing to be part of the trial will be consented and randomised either to:

- The One Stop Vein Clinic (offering same day diagnosis and treatment);  
or
- The normal care pathway

Once patients indicate their consent to participate, their General Practitioners (GP) will be sent a letter informing them of the patient's participation in this study.

Patients declining to partake in the randomised part of the study, but agreeable to complete study questionnaires while continuing down the normal care pathway, will also be consented. Further information will be provided to them when they attend for their clinic appointment and the consenting process will take place when they attend for their subsequent procedure

### **One Stop Vein Clinic Pathway**

Patients attending the One Stop Vein Clinic will be reviewed by the Vascular Surgeon, who will confirm the patient's consent in the trial, then assess the degree of venous disease and fill in the Clinical-Etiology-Anatomy-Pathophysiology (CEAP) classification and Varicose Clinical Severity Score (VCSS). If the patient's symptoms are deemed secondary to venous disease, they will be sent to have a Duplex scan to confirm the presence of the venous disease. The results will be reviewed by the Vascular Surgeons, and if the patients are suitable for endovenous ablation +/- avulsions or UGFS, they will be informed of the findings of the scan and proposed treatment. If they are happy to go ahead with the proposed intervention, they will be consented and transferred to the waiting area to wait for their intervention. If, however, they decline same day treatment, they will be put onto the conventional care pathway.

Another Vascular Surgeon will be carrying out the interventions in an 'office-based' environment under local anaesthetic. Once done, the patients will be asked to fill the Picker patient experience questionnaire. They will subsequently be discharged, similar to current practice, and will be given a diary card to fill for when they return to their normal activities

and work.

Three (3) months post-operatively, they will be asked to fill the AVVQ, CIVIQ, EQ-5D and Picker patient experience questionnaires once more. This will be done by sending them the questionnaires by post.

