### **The Normal Care Pathway,(NCP)**

In the normal care pathway, patients referred by their GP are seen in the outpatient clinic and, if their symptoms are suggestive of varicose vein disease, they are sent to have a venous duplex scan. This usually happens on a different day. Afterwards, they are seen back in the clinic (again on a different day) and, if the scan result suggests venous incompetence amenable to day case treatment, they are added to the waiting list. The eventual procedure takes place some time later (within 18 weeks from referral to treatment). After their procedure, they will be asked to fill a Picker patient experience questionnaire. On discharge, they will be given a diary card to fill for when they return to their normal activities and work. At 3 months post intervention, patients randomised to the normal care pathway will be sent the QoL questionnaires again and asked to fill the AVVQ, CIVIQ, EQ-5D and Picker patient experience questionnaires. As there will be an inherent delay in the NCP pathway we can not use the time from randomisation as many patients will not have received their interventional treatment by then.

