### **Inclusion and Exclusion Criteria**

The inclusion criteria are:

- Adults over the age of 18 years
- Unilateral lower limb symptoms suggestive of venous disease on the referral letter

The exclusion criteria are:

- Recurrent varicose veins
- Known arterial disease or ABPI<0.8
- Current deep vein thrombosis
- Patients who withdraw their consent
- Inability to complete the questionnaire or attend follow up appointments
- Currently enrolled in other venous study

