#### REPORTING PROCEDURES

All adverse events should be reported to the trial management committee via the CI and via the trust datix system.

Depending on the nature of the event the reporting procedures below should be followed.

Any questions concerning adverse event reporting should be directed to the Chief Investigator in the first instance.

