#### *Adverse Events (AE)*

All such events, whether expected or not, should be recorded.

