- Picker questionnaire
- AVVQ, CIVIQ and EQ-5D
- CEAP and VCSS
- Patients given diary card to fill

Day of Treatment:

- Picker questionnaire
- AVVQ, CIVIQ and EQ-5D
- CEAP and VCSS
- Patients given diary card to fill

Follow-up at 3 months:

- Picker questionnaire
- AVVQ, CIVIQ and EQ-5D
- CEAP and VCSS

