## **Appendix 9. Patient Diary**

Please indicate at what stage you were able to return to work and your normal daily activities (the activities you were able to do prior to your treatment)

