**Day I was able to resume my normal activities**

**(please tick one box)**

**Day I returned to work (please tick one box)**

Day of surgery

Day after surgery

2 days after surgery

3 days after surgery

4 days after surgery

5 days after surgery

6 days after surgery

7 days after surgery

8 days after surgery

9 days after surgery

10 days after surgery

>10 days after surgery

•

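### All adverse events must be recorded, but nothing scheduled after discharge asks about them, so harms may be under-recorded; the text and flow chart also disagree on whether the 3-month follow-up is postal

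*Protocol*

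**What the plan says.** **The duty.** Under Adverse Events (AE): "All such events, whether expected or not, should be recorded". Reporting Procedures gives the route once an event is known: "All adverse events should be reported to the trial management committee via the CI and via the trust datix system". The SAE section adds a form to the Chief Investigator within 24 hours.

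**Contact after discharge.** Under Treatment Allocation, patients leave on the day of treatment. Both pathway sections then give them a diary card and, at 3 months, a set of questionnaires. For the One Stop arm: "This will be done by sending them the questionnaires by post". Normal-care patients "will be sent the QoL questionnaires again and asked to fill the AVVQ, CIVIQ, EQ-5D and Picker patient experience questionnaires".

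**The diary (Appendix 9).** "Please indicate at what stage you were able to return to work and your normal daily activities". It has two tick-box columns, one for activities and one for work.

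**The flow chart (before Appendix 1).** Both boxes labelled "Follow-up at 3 months" list CEAP and VCSS alongside the questionnaires. The One Stop Vein Clinic Pathway section has the vascular surgeon complete those two instruments when reviewing the patient in clinic.

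**The concern.** The protocol sets a duty to record every event and says where a known event goes. It does not say when, or by what question, a patient is asked about events after going home. A complication managed by a GP or another hospital then reaches the trial only if someone reports it unprompted.

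Three uses of the data are affected:

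- The criterion for stopping the trial early refers to major adverse effects in either arm, so it needs those effects to be known.
- Cost-effectiveness is a secondary outcome, and the care of complications is a cost.
- The pilot is meant to inform a larger trial, and a low harm count would carry forward into it.

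The second problem needs no assumption. The methods text and the flow chart describe different 3-month follow-ups, and staff cannot carry out both.

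**Working it through.** The protocol has no figure to reproduce here, so the main check compares its sections.

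**1. Does any scheduled form ask about complications?**

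- Diary (Appendix 9): day activities resumed and day work resumed. The last option is more than 10 days. No complication item.
- EQ-5D (Appendix 1): health state on the day of completion.
- AVVQ (Appendix 2): current state or the last two weeks. Pain, painkillers, swelling, discolouration, rash and ulcer overlap with some possible harms, but are mostly worded as features of the veins or leg, not events after a procedure.
- CIVIQ-14 (Appendix 8): leg symptoms and their effects over the past four weeks.
- Societal questions (Appendix 3): income, education, time off and care costs for an appointment.
- Picker: sent at 3 months but not reproduced, so its content cannot be checked. The protocol describes it as a patient experience questionnaire.

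**2. What period do the three reproduced questionnaires cover?** Three months is about 52/4 = 13 weeks. The longest look-back is 4 weeks, and 13 − 4 = 9. So about the first nine weeks after the procedure fall outside all three.

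**3. What other routes exist?** A helpline number in the invitation pack, a letter telling the GP that the patient is in the study, Datix, and the SAE form. Each depends on a patient or clinician coming forward.

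**4. Can the two descriptions of the 3-month follow-up both hold?** The pathway sections have questionnaires sent out. The flow chart adds CEAP and VCSS, which the methods text assigns to a surgeon in clinic. A mailed pack cannot produce them. Either they will be missing at 3 months, or visits are needed that the methods text does not schedule.

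**5. Illustration of size.** The protocol gives no complication rate and no capture rate, so both are assumptions. Let n = 208 per arm (Study Duration & Sample Size), p = true rate of post-discharge complications and a = share captured. Expected recorded events per arm = n·p·a. Probability that an arm records none = (1 − p·a)^n.

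| p | a | Expected per arm | P(none recorded) |
|---|---|---|---|
| 1% | 100% | 2.1 | 12% |
| 1% | 50% | 1.0 | 35% |
| 1% | 25% | 0.5 | 59% |
| 3% | 100% | 6.2 | 0.2% |
| 3% | 50% | 3.1 | 4% |
| 3% | 25% | 1.6 | 21% |
| 5% | 100% | 10.4 | <0.1% |
| 5% | 50% | 5.2 | 0.5% |
| 5% | 25% | 2.6 | 7% |

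For example, with p = 3% and a = 25%: 208 × 0.03 × 0.25 = 1.56, and (1 − 0.0075)^208 = 0.209. Fewer than 208 per arm may be treated, because treatment depends on the scan; the counts would then be lower.

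**The case against.** The best case for the plan is that reporting routes exist. Patients have a helpline, GPs know of their participation, and Datix and the SAE form apply to anything staff hear of. Major events, the kind relevant to stopping, are the likeliest to surface. Several AVVQ items would pick up a problem still present at 3 months, and Picker might ask something relevant. The information leaflet and SAE form are not reproduced, and the page after the SAE section was not in the text read, so what patients are told about reporting problems cannot be judged. Safety is neither a primary nor a secondary outcome.

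Much of this stands, and it rules out several stronger readings that a reader might infer:

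- *That harms will be missed, or that the trial will report none.* The passive routes, and events seen on the day of treatment, make zero capture a worst case. An upper confidence bound calculated from zero recorded events would rest on that worst case.
- *That under-recording favours the One Stop clinic.* The treatment types are common to the trial and the written follow-up is similar in both arms. The documents give no direction of bias.
- *That complication costs are lost altogether.* The protocol does not name its source for healthcare use, and hospital records are not ruled out.
- *That the exclusion for "Inability to complete the questionnaire or attend follow up appointments" proves a 3-month visit is intended.* The normal pathway has a return clinic appointment after the scan, and the wording may mean that.

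The objection does not supply a scheduled enquiry. Nor would following the flow chart settle the matter. VCSS has items on inflammation and ulcers, but CEAP and VCSS describe the leg on the day of examination. A complication that had resolved, or a re-attendance, would still go unasked.

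**Conclusion.** The point holds in a limited form. The protocol requires all adverse events to be recorded, yet its methods text schedules no enquiry about them after same-day discharge. The diary and the three reproduced questionnaires do not fill the gap, and about nine of the 13 weeks lie outside those questionnaires' look-back. Post-discharge harms, mainly those treated elsewhere or resolved before 3 months, may be under-recorded in both arms. That weakens the information behind the stopping criterion and the cost comparison.

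The size cannot be fixed from the protocol. Under assumed rates of 1% to 5% and capture of 25% to 50%, the expected count per arm falls to between a quarter and a half of its true value. At a 1% rate, the chance that an arm records nothing rises from 12% to between 35% and 59%. This also assumes that Picker and the patient leaflet do not already contain a complication enquiry.

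The conflict between the pathway sections and the flow chart over the 3-month follow-up rests on no assumption about rates. Both matters should be corrected; neither invalidates the design.

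**What to change.** 1. Add one short fixed checklist to the 3-month postal pack, identical in both arms: complications since the procedure; GP, emergency or hospital contact because of the leg; any further vein procedure; each with dates. State in the adverse event section that positive answers are entered as AEs or SAEs.
2. Reconcile the two pathway sections with the flow chart on whether the 3-month follow-up is postal or in clinic. If it is postal, remove CEAP and VCSS from the 3-month boxes. If it is in clinic, the pathway sections must say so.

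The cost is one more page in a pack already being sent, some data entry and a minor amendment. The checklist relies on recall over 3 months and captures nothing from patients who do not return the pack, so it reduces under-recording without removing it. It changes data collection only and leaves treatment as it is.

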### **The Normal Care Pathway,(NCP)**

In the normal care pathway, patients referred by their GP are seen in the outpatient clinic and, if their symptoms are suggestive of varicose vein disease, they are sent to have a venous duplex scan. This usually happens on a different day. Afterwards, they are seen back in the clinic (again on a different day) and, if the scan result suggests venous incompetence amenable to day case treatment, they are added to the waiting list. The eventual procedure takes place some time later (within 18 weeks from referral to treatment). After their procedure, they will be asked to fill a Picker patient experience questionnaire. On discharge, they will be given a diary card to fill for when they return to their normal activities and work. At 3 months post intervention, patients randomised to the normal care pathway will be sent the QoL questionnaires again and asked to fill the AVVQ, CIVIQ, EQ-5D and Picker patient experience questionnaires. As there will be an inherent delay in the NCP pathway we can not use the time from randomisation as many patients will not have received their interventional treatment by then.

### **Inclusion and Exclusion Criteria**

The inclusion criteria are:

- Adults over the age of 18 years
- Unilateral lower limb symptoms suggestive of venous disease on the referral letter

The exclusion criteria are:

- Recurrent varicose veins
- Known arterial disease or ABPI<0.8
- Current deep vein thrombosis
- Patients who withdraw their consent
- Inability to complete the questionnaire or attend follow up appointments
- Currently enrolled in other venous study

### **PATIENT SELECTION**

This is a pilot randomised controlled study and patients will be selected following screening of the GP referral letter.

### **CONSENT**

As part of the consenting process, patients will be given three options.

1. Patients wishing to attend the One Stop Vein Clinic and participate in the study will be asked to indicate their consent by signing a consent form and filling in a reply slip. Patients will be randomised either to the One Stop Vein Clinic group or to the Normal Care Pathway (NCP) group.

2. Patients not wishing to attend the One Stop Vein Clinic and participate in the study will be asked to indicate this by filling in a reply slip. They will instead attend the normal care pathway. They will, however, be asked, if agreeable to complete the QoL and Picker patient experience forms.

3. Patients declining either the trial or simple service evaluation will be offered the NCP.

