### **Secondary Outcome**

- Patient satisfaction with the service provided using the Picker patient experience questionnaire both post-operatively and at the 3 months follow-up (One Stop Vein Clinic versus Normal Care Pathway)
- Measure and compare the quality of life scores using EQ-5D, AVVQ and CIVIQ at 0 and 3 months in patients randomised to treatment in the One Stop Vein Clinic with patients randomised to the Normal Care Pathway
- Time from referral to treatment
- Assess the cost-effectiveness of the One Stop Vein clinic compared to the normal care pathway
- Record the time to return to normal activities and to work
- Assess the estimated societal costs

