## **STUDY DURATION & SAMPLE SIZE**

Following screening of their GP referral letter, patients with varicose vein disease will be invited to participate in the study. We estimate that 12-14 patients will be invited on a weekly basis to participate in the study following screening. Out of those, we are anticipating only 8 patients will agree to be randomised to the One Stop Vein Clinic or Normal Care Pathway. If the clinic is held weekly, we estimate recruiting 416 patients over the course of the year (8 patients X 52 weeks).

Statistical analysis suggests that the sample size of 208 patients per group would be able to power a potential phase 3 multicentre randomised controlled trial. Compared to a previous study conducted in our unit which involved 317 patients in total and looked at different quality of life scores and their responsiveness, the coefficient of variation (ratio of standard deviation to mean) was found to increase at the follow-up period and to vary among the different scores used. With a larger sample size as in this pilot study, this variability would be reduced and result in a smaller coefficient of variation when looking at the follow-up scores. Hopefully, this will enable us to identify the QoL score with the least variability and use it as the primary outcome measure in a future Phase 3 study. A primary outcome measure with little variability would provide us with enough information to estimate an adequate sample size for any future randomised controlled trials.

For example, with a sample size of 208 patients and coefficient of variation of 0.5, a 15% reduction in the geometric mean (a measure of central tendency, similar to median) would be required compared to 25% from the Shepherd et al. study. With power at 85%, this would allow us to determine an adequate sample size.

Participants will be followed-up post-procedure for 3 months, including for patients randomised to the Normal Care Pathway (with potentially longer waiting time from referral to treatment). This means that the study period will be about 18 months. With 3 months for study start-up and 3 months to write the study up, the study will last for 24 months.

Approximately 1,000 patients undergo varicose vein procedures at the Imperial College NHS Trust every year.

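### The CONSENT section makes a wish for the One Stop clinic the route into randomisation, while METHODS and the sample-size section ask only for agreement to be randomised; read literally, it risks disappointment bias in the randomised NCP arm

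*Protocol*

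**What the plan says.** The protocol describes entry to the randomised part in two ways.

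**By preference.** CONSENT, option 1, reads "Patients wishing to attend the One Stop Vein Clinic and participate in the study will be asked to indicate their consent", and continues "Patients will be randomised either to the One Stop Vein Clinic group or to the Normal Care Pathway (NCP) group". Option 2 is its mirror image: "Patients not wishing to attend the One Stop Vein Clinic and participate in the study will be asked to indicate this". For these patients, "They will instead attend the normal care pathway", and they may complete the quality-of-life and Picker forms. Option 3 covers patients who decline both the trial and the service evaluation. COST ESTIMATION echoes this framing: it counts about 416 patients as recruited for the one stop clinic and mentions separately those who decline it because they prefer the normal pathway.

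**By agreement.** METHODS reads "Patients agreeing to be part of the trial will be consented and randomised either to" the two pathways, and describes the unrandomised questionnaire group as patients who decline the randomised part. STUDY DURATION & SAMPLE SIZE says "we are anticipating only 8 patients will agree to be randomised to the One Stop Vein Clinic or Normal Care Pathway" out of the 12 to 14 invited each week.

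BACKGROUND reports a survey of 106 patients in which 90% were agreeable to a one-stop clinic, and concludes: "Hence, it appears that patients in our unit have a preference for a one stop clinic". The secondary outcomes include "Patient satisfaction with the service provided using the Picker patient experience questionnaire", collected after the procedure and again at 3 months.

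**The concern.** Wanting one of the two pathways and being willing to accept either are different conditions, and they select different samples. Under the CONSENT wording, a patient enters the randomised part by expressing a wish for the experimental arm. Everyone then randomised to the NCP has been allocated against that wish, and nobody randomised to One Stop has. A patient who has no preference but would accept either pathway has no clear place among the three options as worded.

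This matters because patients will know their allocation (same-day care against several visits), no blinding is described, and Picker, AVVQ, CIVIQ and EQ-5D are all completed by the patient. Part of a difference in favour of One Stop could then reflect disappointment at allocation rather than the service. Disappointed patients may also be less likely to return the 3-month postal questionnaires. Picker is the most exposed because it asks about the experience of care. EQ-5D is less directly exposed, but it feeds the primary QALY outcome. The trial is also meant to inform a larger multicentre trial, so the consent route could be carried forward.

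**Working it through.** **Side-by-side reading**

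| Section | Condition for randomisation | Patients left unrandomised |
|---|---|---|
| CONSENT | Wish to attend One Stop, and participation | Those not wishing to attend One Stop; those declining everything |
| COST ESTIMATION | Recruited for the one stop clinic | Those who decline it and prefer the NCP |
| METHODS | Agreement to be in the trial | Those declining the randomised part |
| STUDY DURATION & SAMPLE SIZE | Agreement to be randomised to either pathway | Not stated |

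The first two rows cannot be equated with the last two. A patient without a preference is eligible under METHODS, but under CONSENT has not expressed the wish that opens option 1. The framing is also more than one stray word, since options 1 and 2 are a matched pair and COST ESTIMATION repeats it.

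**How much a shift would matter at this sample size (illustration)**

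Inputs from the protocol: 8 patients a week × 52 weeks = 416, and 416 / 2 = 208 per group, which agrees with the stated figure. The protocol's power statement is not used here.

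Assumptions, none of them in the protocol: equally good services; an approximately normal score in SD units; a two-sided 5% test; complete data; and a mean shift *d* in the NCP arm due only to disappointment.

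- Standard error of a standardised difference: √(2/208) = 0.098.
- Probability that the test favours One Stop: Φ(*d*/0.098 − 1.96).

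| Assumed *d* (SD) | *d*/SE | Favours One Stop, 208 per arm | Favours One Stop, 166 per arm (80% return, assumed) |
|---|---|---|---|
| 0.1 | 1.02 | 17% | 15% |
| 0.2 | 2.04 | 53% | 45% |
| 0.3 | 3.06 | 86% | 78% |

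Without any shift, this probability would be 2.5%.

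**What rewording can and cannot do**

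If a fraction *p* of the NCP arm prefers One Stop and each such patient shifts by *d*, the arm shifts by *p* × *d*. The literal CONSENT wording sets *p* = 1. If neutral wording gave *p* = 0.9 (an assumption; the survey's 90% were agreeable to the clinic, which is not the same as preferring it), a shift of 0.2 SD would become 0.9 × 0.2 = 0.18 SD, and 53% would become Φ(0.18/0.098 − 1.96) = 45%. Rewording stops the selection; it does not abolish preference.

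On the same assumption, the patients without a preference would number about 0.1 × 208 ≈ 21 per arm, with a standard error of √(2/21) = 0.31 SD. That is enough for description but not for a firm comparison.

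**The case against.** The strongest reply is that CONSENT is loosely drafted and *wishing* was meant as *willing*. The sentence that follows option 1 states the randomisation openly, and METHODS and the sample-size section describe entry neutrally, so a patient without a preference could enter under METHODS. That may well be the intention. It does not remove the point, because CONSENT is the section that sets out the options put to patients, and it gives a different condition from the other two.

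A reader might go further and infer that every NCP patient is refused a stated wish, that the satisfaction ratings are therefore biased, and that preference goes unrecorded. The documents do not support this:

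- Patients under options 2 and 3 attend the NCP by choice. At most, the statement applies to the randomised NCP arm, and only on the literal reading.
- Nor does the whole One Stop arm get what it wished for. The One Stop Vein Clinic Pathway section makes same-day treatment depend on the assessment, the scan and the patient's agreement.
- The text of the reply slip is not available, so whether it records preference cannot be judged. The appendices shown contain no such item.
- The documents give no size for a disappointment effect. The percentages above would apply to any open trial with 208 per arm and the same assumed shift.
- NCP patients first complete Picker after their procedure, which may be up to 18 weeks after referral, and again at 3 months. Disappointment at allocation may have faded by then.
- EQ-5D, AVVQ and CIVIQ ask about health or leg symptoms, not about the service.
- Dissatisfaction with waiting and repeat visits is partly a real effect of the pathway under study.

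All of this stands, as does the fact that Picker is a secondary outcome in a pilot. It reduces the point from demonstrated bias to an avoidable risk.

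**Conclusion.** The protocol contradicts itself on who is randomised. On the literal CONSENT wording, the randomised sample is enriched for preference for the experimental arm: all of the 208 patients randomised to the NCP, and none of those randomised to One Stop, would be allocated against a stated wish. With visibly different pathways, no blinding described and self-reported outcomes, this creates a risk of disappointment bias and of unequal questionnaire return. The risk is chiefly to Picker and possibly to EQ-5D and the QALY outcome.

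Its size cannot be derived from the documents. The figures of 17%, 53% and 86% show only that a shift of 0.1 to 0.3 SD, if it occurred, would matter with 208 per arm. They rest on the assumptions listed in the working. On the neutral reading of METHODS and the sample-size section, the selection disappears and only the preference common to any open trial of an attractive service remains. The point is worth correcting before recruitment, because it determines who is randomised and because preference before allocation cannot be reliably recovered later.

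**What to change.** 1. Reword CONSENT option 1 as *patients willing to be allocated by chance to either the One Stop Vein Clinic or the Normal Care Pathway*, and option 2 as *patients not willing to be randomised*. Bring METHODS, STUDY DURATION & SAMPLE SIZE and COST ESTIMATION into line with that single entry condition.

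2. If the reply slip does not already do so, record pathway preference (One Stop / normal pathway / none) once, before randomisation. Show Picker and EQ-5D results by preference as a descriptive sensitivity table.

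Covariate adjustment should not be presented as removing the bias. Randomisation already balances preference between the arms on average, whereas disappointment arises from the combination of preference and allocation, which a main-effect adjustment leaves in place.

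The cost is a minor consent amendment, one baseline item and one extra table. A few patients attracted only by the clinic may decline, so recruitment could be slightly slower than the 8 per week assumed.
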